8.2 Optison (perflutren lipid microsphere) CEU contrast agent

Rare

headache, nausea and/or vomiting, flushing, dizziness

Very Rare

Pain (which may be severe)**Hypersensitivity episodes have been reported.**

Mild episodes are defined as events that include hives or urticaria, but are not characterized by respiratory compromise, angioedema or reduced blood pressure.

Severe episodes are defined as events that include either respiratory compromise (brochospasm, hypoxemia, stridor, dyspnea), anaphylaxis, angioedema, or reduced blood pressure.

Optison Toxicity Management:

The subject should be advised to report any sudden onset of symptoms and report it to the ultrasound tech. The contrast agent should be stopped immediately if hypersensitivity or other serious AE develops.

For possible hypersensitivity reactions, please stop administration of the contrast agent and use the suggestions provided previously in **section 8.1**.

9. Correlative studies

9.1. CEU methodology

Low-mechanical index power modulation imaging (IE33, Philips Ultrasound) will be performed at a transmission frequency of 1.7 MHz with a phased-array transducer at a mechanical index of 0.15.^{20,30}. We will image the deep forearm flexor muscles (short-axis), the myocardium (3-apical views) and kidney (optional) after establishing a continuous infusion of lipid-shelled octafluoropropane microbubbles (Optison, GE Healthcare), which will be prepared in the following way: 1 vial (0.5ml) diluted into 15-30ml with sterile saline, and infused at a rate of approximately 90-120ml/hr. Adjustment may be necessary to achieve desired imaging effect, but will not exceed manufacturer's dosing recommendation. This dose may be repeated during the CEU if necessary, not to exceed manufacturer's packaging recommendations. Images of the forearm may also be acquired 2 minutes after initiating hand-grip exercise (12 Hz at 50% maximal tension) to assess flow reserve. Images will be acquired for 15 seconds after a destructive (MI 1.0) 5 frame pulse sequence. Time-intensity data fit to the function: $y=A(1-e^{-kt})$ where y is intensity at time t , A is the plateau intensity, and the rate constant is the microvascular flux rate reflecting RBC flux rate^{31,32}. There may be a 30 minute break during the course of the contrast-enhanced ultrasound procedure. Data analysis will take place in the laboratory of [name] (Co-PI) in Portland, OR. Microvascular blood volume (MBV) will be quantified by $(A)/(1.06 \times I_{LV} \times F)$ where 1.06 is tissue density (g/cm^3), and F is the scaling factor for a different infusion rate for I_{LV} (0.3 ml/min) which will be reduced to avoid dynamic range saturation. Quantitative perfusion ($\text{ml}/\text{min}/\text{g}$) will be calculated by the product of MBV and F . Spatial distribution of microvascular flow in skeletal muscle will be determined by using fractal analysis in the spatial domain on parametric images as previously described.

9.2 iNKT cell measurements

iNKT cell measurements will be performed in the lab of [name] (Co-I) in La Jolla, CA. 4 ml whole blood will be collected per time point into vacutainer EDTA tubes and stored at 4°C until shipping in cold containers. A rapid express system that we have

developed will permit all samples to reach [name] laboratory in La Jolla, CA, in 24 hours.

Two methods will be used to identify iNKT cells:

- 1) CD1d tetramers, loaded with the α -GalCer-like glycolipid PBS57 (defined as tetramer⁺CD3⁺)
- 2) 6B11 antibodies (defined as CD45⁺6B11 high)

Concordance between cells identified by CD1d tetramers and 6B11 antibodies is >90%. Further, only cells staining CD45⁺6B11 high will be called iNKT cells, recognizing that our sensitivity for detecting iNKT cells will be lower, but we will have fewer false positives. FACS analysis and counting beads are then used to determine the absolute numbers of iNKT cells and the percent of iNKT cells among all lymphocytes (live, CD45⁺ low side scatter cells).

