Contrast-enhanced ultrasound has the potential to significantly improve our ability to measure the efficacy of drug candidates. It is notable that in multiple previous studies, it has been possible to detect < 10% changes in skeletal muscle vascular perfusion, indicating that contrast-enhanced ultrasound can detect small changes in vascular perfusion¹⁶⁻²⁰. [name] (PI) laboratory has used contrast-enhanced ultrasound to evaluate flow disturbances in the coronary, renal and skeletal muscle microcirculation related to inflammatory diseases and rheologic disorders such as ischemia-reperfusion injury²¹, hyperlipidemia²², insulin resistance²⁰ and endothelial dysfunction²³. Pertinent to sickle cell disease, contrast-enhanced ultrasound is able to not only quantify regional perfusion, but is also able to separately assess tissue capillary blood volume, capillary RBC velocity, and spatial heterogeneity of capillary perfusion. Contrast-enhanced ultrasound is a portable technique that can be performed at bedside in about 5 minutes.

Two separate FDA-approved agents (Definity and Optison) are available to assess skeletal muscle in doses that are within the regulatory agency guidelines. There have been over 3 million administered doses of the microbubble contrast agents with an excellent safety profile, including in very unstable conditions such as myocardial

infarction. The reported incidence of pain associated with Definity is 1.2%⁴⁰; although personal communications with practicing cardiologists suggest that the incidence is much lower. In our studies of patients with SCD, the incidence of pain events per CEU exam was 4.1% (4/97). [name] (Co-PI) has performed studies in a murine model implicating complement deposition on the microbubbles as the mechanism for the pain events associated with Definity⁴¹. In the renal vasculature, the complement-laden microbubbles adhere to the endothelium and generate bradykinin, which alters nociception and causes pain⁴¹. We would like to further evaluate the mechanism of pain in this patient population. Currently, there is no literature to suggest that patients with SCD, or any other pro-inflammatory disorder, are more susceptible to pain reactions due to Definity than other groups. To determine whether complement deposition contributed to the pain events associated with Definity in patients with SCD, we will perform in vivo and flow cytometry analyses on plasma samples.

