4.1 Regadenoson Study Treatment (Milwaukee): To examine the effects of regadenoson on microvascular blood flow, we will administer regadenoson at 1.44 mcg/kg/hr, to 27 evaluable subjects with sickle cell disease ages 18 to 70 years, for 24 hours. Study coordinators will identify participants from rosters of the sickle cell disease clinic populations in Milwaukee. Following informed consent and after confirming eligibility, Subjects will receive infusional regadenoson when they are at baseline (see definition of baseline **section 3.7**). Prior to starting the infusion, a limited functional 2D echocardiogram and signal-average electrocardiogram will be performed. Contrast-enhanced ultrasound, correlative study lab measurements and optional “red and white blood cell” exploratory lab measurements will be obtained at baseline, approximately 6 hours after the infusion starts, and prior to stopping the infusion. A limited functional 2D echocardiogram may also be repeated prior to stopping the regadenoson infusion. Subjects will be monitored for 6 hours after the infusion is complete and will repeat the contrast-enhanced ultrasound measurement at the conclusion of the observation period. Subjects will also be asked to complete a cardiac questionnaire. The primary outcome measure will be a 40% increase in skeletal muscle microvascular blood flow when the 24 hour measurements are compared to the baseline measurements.

4.2 Sickle Cell CEU subjects (Milwaukee): To determine variability in contrast-enhanced ultrasound measurements among adults with sickle cell disease we will also obtain skeletal muscle and myocardial contrast-enhanced ultrasound values, limited functional 2D echocardiograms, a signal-average electrocardiogram, correlative laboratory study blood samples and optional “red and white blood cell” exploratory blood samples, from 30 evaluable subjects with sickle cell anemia at baseline.

Due to variability in an individual’s blood flow, an additional baseline contrast-enhanced ultrasound may be performed at least 7 days later, but within 30 days, when the subject is at baseline, if feasible. The same study procedures, with exception of the signal-averaged electrocardiogram, will also be performed when the subjects are admitted to the hospital for a pain crisis (see definition in **Section 3.7**).

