13.4 Follow-up and Record Retention

The current proposal involves on-going data collection for the duration of the study at each site. The records will be maintained per site policy but at a minimum of two years per FDA requirements.

14. Statistical Considerations

14.1 Description of Endpoints:

14.1.1 Primary Endpoint: Primary outcome measure will be a 40% increase in skeletal muscle microvascular blood flow when 24 hour measurements are compared to baseline in subjects receiving regadenoson.

14.1.2 Secondary Endpoints:

- Secondary outcome measure will be that there will be more complement deposited on lipid microbubbles from the plasma from the subjects with SCD who suffered pain events compared to the other groups.
- Secondary outcome measure will be a 40% increase in skeletal muscle microvascular blood flow when 12 week measurements are compared to baseline in subjects receiving hydroxyurea.
- Decrease in iNKT cell activation as measured by NFkB when 24 hour measurements are compared to baseline in subjects receiving regadenoson.

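### Section 9.1 defines perfusion as MBV × F, so F cancels, the fitted rate constant is never used, and the result is in ml/g, not ml/min/g; probably a notation slip to check and correct

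*Combined protocol and SAP*

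**What the plan says.** Section 9.1 (CEU methodology) builds flow in three steps.

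- **Fit.** Time-intensity data are fitted to y = A(1 − e^(−kt)). A is the plateau intensity, and "the rate constant is the microvascular flux rate reflecting RBC flux rate".
- **Blood volume.** MBV = A/(1.06 × I_LV × F). The 1.06 is tissue density in g/cm³, and F "is the scaling factor for a different infusion rate for" I_LV, whose infusion rate is given as 0.3 ml/min.
- **Perfusion.** Quantitative perfusion, labelled ml/min/g, "will be calculated by the product of MBV and F".

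The contrast agent for imaging is "infused at a rate of approximately 90-120ml/hr", and the section adds: "Adjustment may be necessary to achieve desired imaging effect".

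The background says the technique can "separately assess tissue capillary blood volume, capillary RBC velocity, and spatial heterogeneity of capillary perfusion".

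The endpoint sections rely on the flow value without defining it. Section 4.1 states: "The primary outcome measure will be a 40% increase in skeletal muscle microvascular blood flow". Section 14.1.1 says the same, and section 14.2 names the change in that flow from baseline to 24 hours. None of the three gives a formula or a unit.

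**The concern.** MBV already has F in its denominator, so multiplying by F returns the expression to what it was before the infusion-rate correction. The product contains no quantity with a time unit, yet it is labelled per minute. The one fitted quantity that does have a time unit, the rate constant, is estimated and then not used. The background treats blood volume and red-cell velocity as separate components; the written rule keeps the first and drops the second.

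Because sections 4.1, 14.1.1 and 14.2 give no formula, section 9.1 is by inference the definition of the primary endpoint. Someone who programmed the endpoint from the document would test a change in blood volume under the name of blood flow, and would miss any effect of regadenoson on flux rate. The infusion-rate correction would also be lost. That alters absolute values at every visit, and alters within-subject percentages if F differs between visits.

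**Working it through.** **Inputs, all from section 9.1:** A (plateau intensity), k (rate constant, 1/time), 1.06 g/cm³, F (infusion-rate scaling factor), I_LV. The section does not define I_LV in words. I take it as an intensity on the same scale as A. The cancellation of F and the absence of k do not depend on that reading; the unit ml/g does.

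**1. The rule as written**

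MBV × F = [A/(1.06 × I_LV × F)] × F = A/(1.06 × I_LV)

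Numerical check with assumed A = 10 and I_LV = 50:

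| F | MBV | MBV × F |
|---|---|---|
| 1 | 0.1887 | 0.1887 |
| 5 | 0.0377 | 0.1887 |
| 10 | 0.0189 | 0.1887 |
| 20 | 0.0094 | 0.1887 |

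F has no influence on the result.

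**2. Units**

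A/I_LV has no unit. Divided by g/cm³ it gives cm³/g = ml/g. The stated ml/min/g is not reproduced. Giving F a unit of its own does not help, because it cancels whatever its unit.

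**3. The rule with the rate constant**

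MBV × k = A × k/(1.06 × I_LV × F)

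The unit is (ml/g) × (1/min) = ml/min/g, which matches the label and keeps F. If k is fitted per second, a factor of 60 is needed.

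**4. Effect on the change from baseline, I_LV and F the same at both visits**

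Ratio with k = (A ratio) × (k ratio). Ratio as written = A ratio. The pairs below are illustrative; each is a true rise of 40%.

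| A ratio | k ratio | Product | With k | As written |
|---|---|---|---|---|
| 1.00 | 1.40 | 1.40 | +40% | 0% |
| 1.183 | 1.183 | 1.40 | +40% | +18.3% |
| 1.40 | 1.00 | 1.40 | +40% | +40% |
| 0.80 | 1.75 | 1.40 | +40% | −20% |
| 1.60 | 0.875 | 1.40 | +40% | +60% |

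The last two rows show that the written rule can fall outside 0% to 40% when A or k falls.

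**5. Effect if F differs between visits**

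Assumptions, none stated in the plan: F = muscle infusion rate/0.3 ml/min; equal dilution; A proportional to infusion rate; I_LV unchanged.

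- 90 ml/hr = 1.5 ml/min, so F = 1.5/0.3 = 5.0
- 120 ml/hr = 2.0 ml/min, so F = 2.0/0.3 = 6.67

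With no true change in flow, A/F is constant and the rule with k shows 0%. The written rule shows 6.67/5.0 = 1.33 (+33%) for 90 then 120 ml/hr, and 5.0/6.67 = 0.75 (−25%) for the reverse. If F is the same at both visits, losing it does not change the percentage.

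**The case against.** The strongest reply is that this turns on one character in a symbol-heavy sentence. The other terms of the fit have their symbols beside their definitions, but the rate constant has none, so a symbol may have been lost in converting the PDF to text and another misread as F. If the source page shows the rate constant in the perfusion sentence, there is no error. That stands, and it is why checking the page comes first. Against it, F reads the same way in the denominator, in its definition and in the product, so the text gives no positive sign that only the last one was misread.

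The second reply is that the intended meaning is plain. The stated unit, the fitted flux rate and the background all point to MBV × k, one laboratory analyses all the images, and the fit cites published methods. This also stands as to likely practice: the document does not show that flow is, or would be, computed wrongly. It does not rescue the sentence, because a written rule for the primary quantity should yield its own stated unit and be reproducible by someone outside that laboratory.

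Third, the percentages rest on assumed values, and the infusion-rate example needs several assumptions at once, including equal dilution when section 9.1 allows 15 to 30 ml. That is fair. They show what literal use could do, not what is expected in this trial.

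**Conclusion.** The concern holds. As the text reads, the only flow formula reduces to A/(1.06 × I_LV), omits the rate constant, discards the infusion-rate correction and gives ml/g where ml/min/g is stated. The algebra needs no assumption; the unit needs only that A and I_LV share an intensity scale.

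The practical size depends on how a change in flow divides between A and k, which the documents do not say. In the illustrative cases, a true 40% rise registers anywhere from −20% to +60%, and as 0% when it comes wholly from k. A notation slip is the likely explanation. The point should be fixed because the formula underlies the primary endpoint, but it is not evidence of a faulty measurement. Confidence is medium, since the source page could show a different symbol.

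**What to change.** 1. Check the symbol in the perfusion sentence of section 9.1 in the source PDF. If it is already the rate constant, that sentence needs no change.
2. If it is F, restate the sentence as perfusion (ml/min/g) = MBV × k, where k is the fitted rate constant per minute (multiply by 60 if it is fitted per second).
3. Name k where the fit is described, and keep F only in the MBV denominator.
4. State in section 14.1.1 that the primary endpoint is this perfusion value in skeletal muscle.

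The cost is one corrected sentence and one named symbol in 9.1, and one cross-reference in 14.1.1. No new data are needed.

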9.3 Limited Functional 2D Echocardiogram

All patients will undergo limited functional rest 2D echocardiography to assess for patent foramen ovale (PFO), atrial septal defect (ASD), right-to-left cardiac shunts, and aortic arch diameter. Right ventricular (RV) and left ventricular (LV) and valvular function will also be assessed. The following views will be used for assessment: parasternal long axis (PLAX), parasternal short axis (PSAX), subcostal, and suprasternal. Color flow Doppler will be used across all valves to assess regurgitation. The LV ejection fraction will be calculated according to the "method of discs". Normal LV function will be defined as an LVEF > 55%. Left atrial area and volume and right atrial volume will be measured at end systole using the apical 4-chamber view, as well as apical 2-chamber, and apical 3-chamber views. RV areas at end-diastole and end-systole will be determined in the apical 4-chamber view, as well as apical 2-chamber, and apical 3-chamber views. The tricuspid regurgitant jet velocity will be recorded as the highest value obtained with a good quality Doppler envelope from either modified apical 4-chamber or parasternal views. Tissue Doppler imaging (TDI) will also be performed to obtain the MV annulus in the medial/lateral view, and the TV annulus in the lateral view. Data analysis will take place in the laboratory of [name] (Co-PI) in Portland, OR.

9.4 Signal-average Electrocardiogram

A signal-averaged electrocardiogram (SAECG) is a more detailed type of 12-lead ECG, during which multiple tracings are obtained over a period of approximately 10-

20 minutes. The subject will be asked to lie as still as possible for the duration of the procedure, while the ECG leads are placed, and the cardiac rhythms are recorded. Three techniques will be used to analyze the signals, including temporal signal averaging, spatial signal averaging, and spectral analysis. Temporal signal averaging, averages a number of QRS complexes over time³⁴. Beats are detected by a computer algorithm, based on voltage thresholds or other criteria, then aligned by a constant feature of the signal, the "fiducial"³⁵. Once beats have been aligned, their arithmetic mean is taken. This process diminishes random noise that is not synchronized to the QRS complex. ECG spatial averaging involves the summation and averaging of electrical potentials simultaneously recorded from multiple pairs of closely spaced electrodes³⁶. This process allows a real-time, beat-by-beat analysis of individual QRS complexes, but requires electrical shielding of the patient and equipment. The advantage of this technique over temporal signal averaging is that it allows assessment of irregular rhythms with changing conduction. Spectral analysis considers the QRS complex (or P-wave) to be composed of multiple simple waveforms, typically sinusoids. Spectral analysis thus decomposes the QRS complex or P-wave into these constituent signals, represented by component frequencies and corresponding phase and amplitudes^{37 38}. Spectral decomposition will be performed using Fourier analysis³⁹.

9.5 Exploratory study of inflammatory markers

Since inflammation is known to promote vascular occlusion of sickle erythrocytes, the hallmark of a sickle cell pain event, measuring markers of inflammation at baseline and during a vaso-occlusive crisis may provide insight into the mechanism of inflammation, as it relates to sickle cell vaso-occlusion. Additionally, measuring inflammatory markers before and after administration of regadenoson may provide further evidence about the effects of regadenoson on sickle cell vaso-occlusion. Based on mouse studies we expect that an effective concentration of regadenoson will decrease plasma levels of IFN-gamma, certain chemokines and various other proinflammatory mediators.

Samples will be collected from participants in Milwaukee, in the Regadenoson Arm, Sickle Cell CEU Arm, Healthy Control Arm, and Sickle Cell Control Arm at baseline, and 24 hours after baseline, and/or the start of regadenoson infusion, for measurement of markers of inflammation. Samples will be collected in 4 mL vacutainer tubes with EDTA. They will be spun for plasma, transferred to anonymized plastic cryovials and stored at -80°C or below until ready for analysis. The samples will be destroyed after the analysis is completed.

9.6 Exploratory studies of “red and white blood cell” blood flow adhesion and leukocyte activation (optional)

Samples will be collected optionally from participants in Milwaukee in all study arms (with exception of the Technique Optimization Controls Arm). Up to 10ml whole blood will be collected into anticoagulated vacutainer tubes, spun for serum and plasma separation, and the supernatant transferred to anonymized cryovials and stored at -80°C or below until ready for analysis. The pellets (non-plasma or serum fraction) of the vacutainer tubes may be used to isolate erythrocyte and leukocytes (see description below), for further examination in this study. Any remaining samples will be destroyed after the study analysis is completed.

A flow adhesion assay of isolated blood cells (erythrocytes or leukocytes) will be performed under conditions of controlled flow, to determine red cell or leukocyte rolling and adhesion. For this assay, we will count how many blood cells become adherent or roll along the surface of the flow chamber. Furthermore, we may examine red cell or leukocyte physiology or structural characteristics, such as red cell stiffness of membrane or flow cytometry studies. Sample and data analyses will take place at the lab of [name], at the Blood Research Institute in Milwaukee, WI.

9.7 Exploratory Study of complement deposition on Definity microbubbles in vivo (optional)

Complement deposition on the surface of lipid microbubbles will be compared between samples collected in subjects with SCD who had pain events associated with Definity (n=4), patients SCD who did not have a pain event (n=10) and healthy African American controls (n=10). We will collect up to 4ml whole blood into anticoagulated tubes, and spin for plasma, transfer to anonymized cryovials, and store at -80C until ready for analysis. Samples will be analyzed at the laboratory of [name] in Portland, OR.

In [name] laboratory in Portland, plasma will be incubated with lipid microbubbles and then flow cytometry will be performed to measure surface complement deposition on the microbubbles. Approximately 4ml blood will also be collected for isolation of serum and analyzed for levels of circulating complement (C3, C4, CH50) at a clinical laboratory.

10. Subject Remuneration

